Subjects will be required to make three visits (Day 30 Visit, Day 60 Visit, and Day 90 Visit) to the investigational site. Each visit will cover 2 consecutive days on site. For Day 30 Visit, the subject will check-in at approximately 08:00 AM on Day 30, and will check-out on Day 31. For Day 60 Visit, the subject will check-in at approximately 08:00 AM on Day 60, and will check-out on Day 61. For Day 90 Visit, the subject will check-in at approximately 08:00 AM on Day 90, and will be discharged on Day 91 after having performed all the safety examination procedures.

Twenty four-hour urine will be collected at each ambulatory visit on Day 30 Visit, Day 60 Visit, and Day 90 Visit at the site. The end of the 24-hour urine collection for Day 90 Visit will end in the morning on Day 91 at 09:00 AM.

On Day 30, Day 60, and Day 90, subjects in the THS 2.2 Menthol and mCC arms will be allowed to use their assigned product from approximately 08:00 AM to 23:00 PM. Smoking/product use before 08:00 AM on Day 30, Day 60 and Day 90 are not restricted. On Day 31, Day 61, product use will be allowed from 06:30 AM. The end of the exposure period will be fixed at Day 90 11:00 PM.

The use of THS 2.2 Menthol will be strictly forbidden for subjects in the mCC or SA arms.

On the day of discharge from Day 90 Visit (from Day 90 11:01 PM until time of discharge of Day 91), subject will be discharged from the investigational site after all safety examination procedures have been conducted.

Subject will not be withdrawn from the study for the use of nicotine/tobacco-containing products other than the assigned product/regimen. Subjects will record in a product use electronic diary any use of CC (menthol or non-menthol), NRT, or other nicotine/tobacco-containing products.

During the confinement and ambulatory settings:

- Subjects in the SA arm will be provided with support including psychological support as requested by the subject or considered necessary by the Investigator or study collaborator.
- During the study, any subjects who want to quit smoking will be encouraged to do so, will be referred to medical services and will be withdrawn from the study. This is applicable for all subjects during screening to the baseline period and for subjects allocated to THS 2.2 Menthol or mCC arms during the exposure period.
- The safety follow-up period (from time of Discharge from Day 91 until Day 119):

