6.2 Use of Investigational Product(s)

Subjects will never be requested or forced to smoke and will be free to stop smoking at any time during the study. The study is designed as an *ad libitum* use study. During the screening period, subjects will be allowed to smoke according to their smoking habits except during the procedures of the screening Visit at the discretion of the site.

During the confinement period product (mCC or THS 2.2 Menthol) use will generally be allowed between 06:30 AM to 11:00 PM.

During the ambulatory period, there will be no smoking/product restriction except on Day 30 Visit, Day 60 Visit, and Day 90 Visit: on Day 30, Day 60, and Day 90: product use will be allowed from 08:00 AM to 23:00 PM and during the Visit. Smoking/product use before 08:00 AM on Day 30, Day 60 and Day 90 are not restricted. On Day 31, Day 61, product use will be allowed from 06:30 AM. In the morning of Day 91 after the end of exposure ambulatory period (11:00 PM on Day 90), subjects will not be allowed to smoke CC until CYP2A6, cough and MNWS questionnaires and spirometry have been done on site. The use of THS 2.2 Menthol will be strictly forbidden for subjects in the mCC or SA arms.

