6.2.3 Exposure Period

During the exposure confinement period until the time of Discharge on Day 6, subjects will not be allowed to use any nicotine/tobacco-containing products other than their assigned product/regimen. On Day 6, when the safety procedures of discharge will be conducted, the use of product (THS 2.2 Menthol or mCC) will be allowed but after CYP2A6, cough and MNWS questionnaires and spirometry have been done. Smoking will not be allowed in the SA arm.

During the exposure ambulatory period, subjects will be instructed to continue using exclusively their assigned product/regimen. The use of any CCs (menthol or non-menthol) or nicotine/tobacco-containing products other than the product/regimen the subject is assigned to must be documented in the daily product use electronic diary. Subjects in the SA arm will be instructed to abstain from smoking.

In the morning of the Day 91, smoking will not be allowed to smoke until CYP2A6, cough and MNWS questionnaires and spirometry have been conducted at the clinic. After, subjects will be allowed to smoke. On Day 91, safety procedures of Discharge will be conducted prior the time of Discharge of the subject from the site (completion of the study).

During the study, any subjects who is willing to stop smoking will be referred for further treatment as per the standard of care in the country in which the study is conducted.

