7.7.2 Urine samples

Spot urine samples will be used for the urine drug screen, urine cotinine screen, urine pregnancy test, and safety urinalysis.

24-hour urine collection during the confinement period:

For the 24-hour urine collection, subjects will empty their bladders shortly before 06:30 AM on the study day indicated in the Schedule of Events (Appendix 1). The collection period starts at 06:30 AM and ends on the following day at 06:29 AM. Shortly before 06:29 AM, after nearly 24-hours of urine collection, subjects will empty their bladder again and this urine will be used as the final portion of the 24-hour urine sample.

At time of Discharge on Day 6, subjects will empty their bladder shortly before 06:29. This will be the last urine portion for the 24-hour urine for the Day 5 dot mark in the Schedule of Events.

24-hour urine collection during the ambulatory period:

Twenty four-hour urine fraction will be collected on Day 30 Visit, Day 60 Visit, and Day 90 Visit) at site.

Subject will be asked to come at site at around 08:00 AM on Day 30, Day 60 and Day 90 and will remain overnight on site until respectively Day 31, Day 61, and Day 91. Subject will be asked to empty his bladder on Day 30, Day 60, and Day 90 shortly before 09:00 AM minutes (this urine will be discarded). Then collection period will start at 09:00 AM \pm 20 minutes. After nearly 24-hours of urine collection the day later at 08:59 AM \pm 20 minutes, subjects will empty their bladder again and this urine will be used as the final portion of the 24-hour urine sample.

For both confinement and ambulatory periods;

All urine passed during the sampling period must be collected and put into the sampling bottle, with the exception of about 10 mL for the spot urine tests (described above). No urine

must be passed into the toilet. The volume of 24-hour urine, the start and the end time of urine collection will be recorded by the study collaborators.

For assessment of urine BoExp, creatinine for normalization of urine BoExp, 8-epi-PGF2 α and 11-TBX-B2, sample bio-banking and urine mutagenicity, aliquots from the 24-hour urine collection will be taken. In the Schedule of Events for the 24-hour urine collection (see Appendix 1), the dot corresponds to the day on which the 24-hour urine collection period starts. For example, for NEQ measured at Day 30 Visit in the 24-hour urine collection that starts on Day 30 and ends later on Day 31.

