08:00 AM-11:15 PM		Collection of empty/partially used menthol THS tobacco stick packs	At any time of the day For accountability Partially used packs will be returned to the subject
08:00 AM-11:15 PM		Collection of tobacco plugs from each used Menthol Tobacco Stick	All day For further analysis

Abbreviations: 8-epi-PGF2 α = 8-epi-prostaglandine F2 α ; 11-DTX-B2 = 11-dehydro-thromboxane B2; AE = adverse event;; BMI = body mass index; BoExps = biomarkers of exposure; mCC = conventional cigarette(s); CO = carbon monoxide; COHb = carboxyhemoglobin; CYP = cytochrome P450 enzyme; ECG = electrocardiogram; HbA1c = hemoglobin A1c; hs-CRP = high-sensitive C-reactive protein; HDL = high density lipoprotein; HST = human smoking topography; LDL = low density lipoprotein; MCEQ = Modified Cigarette Evaluation Questionnaire; MNWS = Minnesota Nicotine Withdrawal Scale; QSU = Questionnaire of Smoking Urges; SAE = serious adverse event; sICAM-1 = soluble inter-cellular adhesion molecule; TG = triglycerides; THS = tobacco heating system; WBC = white blood cell count.

Time	Blood sample	Procedures	Additional information
Start of procedure		Day 91	
	√	AE/SAE questioning; Concomitant medication CYP2A6 activity in plasma	At any time during the day Has to be done prior to smoking

Time	Blood sample	Procedures	Additional information
Start of procedure		Day 91	
		Assessment of cough	To be done no later than 10:00 AM Has to be done prior to smoking
		MNWS questionnaire	To be done no later than 10:00 AM Has to be done prior to smoking
		Spirometry without short-acting bronchodilator	Has to be done prior to smoking
08:59 PM ± 20 min		End of urine collection and urine sample to be taken from the 24-hour urine after final portion of urine has been added to Day 90 sampling bottle	BoExp (primary, secondary, and NEQ), creatinine, Ames mutagenicity Urine biobanking Risk markers: 11-DTX-B2 and 8-epi-PGF2α
	√	Clinical laboratory parameters (hematology, clinical chemistry)*, and risk markers (s-ICAM-1, hs-CRP, fibrinogen, homocysteine, LDL, HDL, TG, HbA1c)	Sample to be collected after at least 10 hours of fasting. *Blood glucose, TG, TC, WBC, and platelet count from safety to be evaluated also as risk markers
	√	Bio-banking for transcriptomics	Sample to be collected after at least 10 hours of fasting If consent is obtained
	√	Bio-banking for BoExp/risk markers in serum/plasma	Sample to be collected after at least 10 hours of fasting If consent is obtained
Before 10:00AM		Breakfast	

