**Table 1 Definition of Study Arms**

Study arm	Number of subjects
THS 2.2 Menthol	80
mCC	40
Smoking abstinence	40

However, one of the sites was closed down after a good clinical practice failure, and 160 subjects were randomized at the Tokyo Heart Centre site along with those subjects randomized at the Seisukai site prior to the site being shut down.

This is an *ad libitum* smoking study. In general, smoking/product use during the confinement period will be allowed between 06:30 AM and 11:00 PM. During the ambulatory period, there will be no smoking/product use restriction except during the three visits on site (Day 30 Visit, Day 60 Visit, and Day 90 Visit), when product use will be allowed from 08:00 AM to around 23:00 PM on Day 30, Day 60, and Day 90. Smoking/product use before 08:00 AM on Day 30, Day 60 and Day 90 are not restricted. During the second day of the Day 30 and Day 60 Visits, product use will be allowed from 06:30 AM onwards. On the second day of the Day 90 Visit, product use will be allowed after the CYP2A6 activity, MNWS and cough questionnaires and spirometry have been performed until time of discharge.

The Screening Visit will be conducted within 4 weeks prior to Admission to the investigational site (Day -30 to Day -3). Screening procedures do not necessarily have to be conducted on the same day. During the Screening Visit the study collaborator will demonstrate the use of THS 2.2 Menthol.

Prior to enrollment on Day -2, as the last procedure of the eligibility assessments, subjects will have a product test of the THS 2.2 Menthol (use of up to 3 THS Menthol Tobacco Sticks). In female subjects, the THS 2.2 Menthol product test will only be done after pregnancy is excluded by a negative urine pregnancy test. Enrollment takes place after all inclusion and exclusion criteria have been satisfactorily met. Only subjects willing and able to use the product will be enrolled in the study.

Subjects are admitted and enrolled on Day -2, but not randomized until Day 0. From Day -2 to Day 0, all subjects continue smoking their single preferred brand of mCC and baseline values will be recorded. On Day 0, subjects will be randomized to one of the 3 study arms (Table 1). Subjects will be informed of their product allocation by the study site staff on Day 1 prior to 06:30 AM.

The exposure period (from Day 1 06:30 AM until time of Discharge on Day 91) will include both the exposure in confinement and the exposure in the ambulatory setting.

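### Protocol Table 18 prints 08:59 PM for the end of the Day 90 urine collection where other sections give 08:59 or 09:00 AM, and the Day 91 release to smoke is not tied to that closing

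*Protocol*

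**What the plan says.** **Closing time of the bottle.**
- Protocol synopsis, repeated in 4.1: "The end of the 24-hour urine collection for Day 90 Visit will end in the morning on Day 91 at 09:00 AM".
- Protocol 7.7.2: "Then collection period will start at 09:00 AM" (± 20 minutes), and "After nearly 24-hours of urine collection the day later at 08:59 AM" (± 20 minutes) the subject gives the last portion.
- SAP Table 18: 08:59 AM ± 20 minutes for Days 31, 61 and 91.
- Protocol Table 18 (Day 91) and Table 17 (Days 31 and 61): 08:59 PM ± 20 minutes.

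**Release to smoke on Day 91.**
- Protocol 6.2: "subjects will not be allowed to smoke CC until CYP2A6, cough and MNWS questionnaires and spirometry have been done on site".
- Protocol 6.2.3: "In the morning of the Day 91, smoking will not be allowed to smoke until CYP2A6, cough and MNWS questionnaires and spirometry have been conducted", followed by "After, subjects will be allowed to smoke". Protocol 6.6.1.2 lists the same four procedures.
- SAP 6.1: "On the second day of the Day 90 Visit, product use will be allowed after the CYP2A6 activity, MNWS and cough questionnaires and spirometry".
- For cough and MNWS, protocol Table 18 gives a latest time but no earliest: "To be done no later than 10:00 AM Has to be done prior to smoking".

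**Exposure and its recording.** The protocol ends the exposure period at 11:00 PM on Day 90, and 6.2.3.1 asks for exclusive THS 2.2 Menthol use only until then. Under 6.2.3.3 the SA arm abstains until discharge on Day 91. The diary (7.8.1) stops at 11:00 PM on Day 90. The SAP (Sections 4 and 6.1) runs the exposure period to discharge on Day 91. Protocol 6.2.5 places freedom to return to own cigarettes in the follow-up after discharge.

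**The concern.** There are two separate weaknesses.

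First, an operative site schedule contradicts the rest of the plan by 12 hours. A site that followed Table 18 would keep the bottle open into the evening of Day 91. SAP 7.1.1 computes quantity excreted as concentration times volume, so a longer collection raises it directly. SAP Table 16 also treats collection times outside a 30-minute window as a major deviation. Such a subject could be lost from the PP Set and so from the primary Total NNAL analysis.

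Second, no section makes the Day 91 release wait for the final void. In confinement the order is set out: protocol Table 16 closes the Day 5 bottle at 06:29 AM and starts product use at 06:30 AM. On Days 31 and 61 product use does overlap the open bottle, but the instruction to use THS 2.2 Menthol exclusively still holds. Only Day 91 combines an open bottle, a lapsed instruction (on the protocol's wording) and a release to conventional cigarettes. Cigarettes may be at hand, because 6.1.2 asks subjects to bring their own to these visits without limiting this by arm. A cigarette smoked then escapes the diary on which SAP Table 16 bases ambulatory compliance. Exhaled CO and COHb are taken on Day 90 and would miss it too.

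**Working it through.** **1. Length of the collection.** The stated length is 24 hours.
- 09:00 AM on Day 90 to 08:59 AM on Day 91 = 23 h 59 min, which reproduces it.
- 09:00 AM on Day 90 to 08:59 PM on Day 91 = 35 h 59 min, 12 hours more.
- At a steady excretion rate, quantity excreted would be 36/24 = 1.5 times too high. Creatinine-adjusted concentrations do not scale with volume in this way.

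**2. Does the release depend on the bottle?** Protocol 6.2, 6.2.3 and 6.6.1.2 and SAP 6.1 each list CYP2A6, cough, MNWS and spirometry. None lists the final void. No clock time is given for the release, so it may fall before or after 08:59 AM.

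**3. Size of a possible contribution with the AM close.** For c cigarettes smoked h hours before closing and half-life T:
- fraction reaching the bottle f = 1 − 2^(−h/T);
- addition relative to the mCC level = (c/20) × f;
- rise relative to the THS level = addition / (THS:mCC ratio).

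From the documents: Total NNAL half-life 10 to 15 days, and an average of at most 24 h for the Day 5 primary markers (protocol 4.2); planning ratios 0.30 for Total NNAL, 0.15 for MHBMA and 0.07 for S-PMA, the last from the second planning study (protocol Tables 19 to 21).

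Assumed: 20 cigarettes a day as the mCC level, 1 to 3 cigarettes smoked 1 to 2.5 h before closing, a 6 h half-life for the short-lived case, and Day 5 planning ratios carried to Day 90.

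| Marker | Low case (c = 1, h = 1) | High case (c = 3, h = 2.5) |
|---|---|---|
| Total NNAL, T = 15 d (low) or 10 d (high), ratio 0.30 | f = 0.0019; rise 0.03% | f = 0.0072; 0.15 × 0.0072 = 0.00108; rise 0.36% |
| T = 24 h, ratio 0.30 | f = 0.0285; rise 0.5% | f = 0.0697; rise 3.5% |
| T = 24 h, ratio 0.15 | f = 0.0285; rise 0.95% | f = 0.0697; rise 7.0% |
| T = 6 h, ratio 0.15 | f = 0.1091; rise 3.6% | f = 0.2508; 0.15 × 0.2508 = 0.0376; rise 25% |

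An intermediate case is two cigarettes, 1.5 h and 0.75 h before closing, at T = 6 h: 0.159 + 0.083 = 0.242 cigarette-equivalents, and 0.242/20 = 1.2% of the mCC level. Relative to THS this is 0.0121/0.15 = 8% for MHBMA and 0.0121/0.07 = 17% for S-PMA. A MHBMA THS:SA ratio planned at 1.00 would read about 1.08. Relative size varies inversely with the ratio, so the 25% belongs to a ratio of 0.15.

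**4. Primary endpoint.** For Total NNAL, SD = √ln(1 + 0.60²) = 0.5545, SE = 0.5545 × √(1/40 + 1/40) = 0.124, and ln(0.50/0.30)/0.124 − 1.96 = 2.16, which gives power 98.5%. Adding 0.001 to the ratio of 0.30 gives 98.4%. The same method reproduces the planned joint power at a 50% reduction (94.3% against 94%, and 98.2% against 98%).

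**The case against.** - **The PM time looks like a misprint.** The Table 18 row describes a 24-hour collection and stands above breakfast before 10:00 AM and the afternoon discharge procedures. Start and end times are recorded, and the SAP's window would expose a 36-hour bottle. This stands: a reader might infer that the sample really is collected over 36 hours, and the documents do not support that. It remains an entry in a working schedule that needs correcting.
- **Table 17 cannot touch the Day 90 sample.** Correct. It covers Days 31 and 61 only.
- **Overlap is not scheduled.** Cough and MNWS may run to 10:00 AM and subjects cannot all be assessed at once, so release may follow the void. This stands. A reader might infer that cigarette exposure will enter the sample; the documents show only that nothing prevents it.
- **The SAP reads differently.** It releases product use rather than conventional cigarettes and ends exposure at discharge. On that reading, THS 2.2 Menthol use before the final void is assigned exposure, not contamination. This is fair, and it shows that the two documents, and protocol 6.2.5, need reconciling.
- **The plan already tolerates some cigarettes.** The PP Set keeps THS subjects with up to 2 in a day and an average of up to 0.5 per day. True, so the bottle was never guaranteed free of cigarettes. But those cigarettes are recorded and count towards compliance; any on Day 91 are not.
- **The sizes are assumed.** Cigarette counts, smoking times and the 6 h half-life are not in the documents, and the formula treats absorption and excretion as immediate, which overstates the contribution. This stands.

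**Conclusion.** Both points hold as minor defects. The closing time of the ambulatory collections is contradicted by 12 hours in protocol Tables 17 and 18. The Day 91 release also permits smoking before the Day 90 bottle is closed, without any record of it.

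A reader might infer that the primary result is at risk. The documents do not support that. With the AM close, Total NNAL rises by about 0.03% to 0.4% and its power is essentially unchanged. The Day 5 endpoints are not involved, and Day 90 COHb and exhaled CO are taken before the release.

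The exposed endpoints are the short-lived urinary markers analysed at Day 90 as secondary, mainly in the THS:SA comparison, where SA subjects are told to abstain until discharge. The bias works against THS 2.2 Menthol: from under 1% to about 7% for a 24 h half-life, and about 4% to 25% for an assumed 6 h half-life at a ratio of 0.15. These figures apply to a subject who smokes before the final void; the effect on the arm is diluted by the share who do. They rest on assumed cigarette counts, times and half-lives, and on Day 5 planning ratios carried to Day 90.

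**What to change.** 1. Reconcile the 08:59 PM entries in protocol Tables 17 and 18 with protocol 7.7.2 and SAP Table 18.
2. In protocol 6.2, 6.2.3 and 6.6.1.2 and SAP 6.1, state that the final void of the Day 90 collection precedes the Day 91 release.
3. Reconcile the protocol (exposure ends at 11:00 PM on Day 90, conventional cigarettes released) with the SAP (exposure ends at discharge on Day 91, product use released) and with protocol 6.2.5, so that it is clear what exposure the last hours of the bottle represent.

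The cost is wording only. Some subjects would wait somewhat longer on one morning.

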CC	Conventional cigarette(s)
CD	Compact disc
CEMA	2-cyanoethylmercapturic acid
CO	Carbon monoxide
COHb	Carboxyhemoglobin
COPD	Chronic obstructive pulmonary disease
CRA	Clinical Research Associate

Data and information contained in this document are considered to constitute trade secrets and confidential commercial information, and the legal protections provided to such trade secrets and confidential information are hereby claimed under the provisions of applicable law. No part of this document may be publicly disclosed without the written consent of Philip Morris Products S.A.

CRO	Contract Research Organization
CSR	Clinical study report
CTCAE	Common Terminology Criteria for Adverse Event and Common Toxicity Criteria
CTMS	Clinical Trial Management System
CV	Coefficients of variation
CYP1A2	Cytochrome P450 1A2
CYP2A6	Cytochrome P450 2A6
DMP	Data management plan
ECG	Electrocardiogram
eCRF	Electronic Case Report Form
EHCSS	Electrically heated cigarette smoking system
EOS	End of Study
ePRO	Electronic patient report outcome
FAS	Full analysis set
FDA	Food and Drug Administration
FEV ₁	Forced expiratory volume in 1 second
FTND	Fagerström Test for Nicotine Dependence
FVC	Forced vital capacity
GCP	Good Clinical Practice
GGT	Gamma-glutamyl transferase
GVP	Gas vapor phase
HbA1c	Hemoglobin A1c
HDL	High density lipoprotein
HEMA	2-hydroxyethyl mercapturic acid
HIV	Human immunodeficiency virus
HMPMA	3-hydroxy-1-methylpropyl mercapturic acid
PHPCs	Harmful and potentially harmful constituents
hs-CRP	High-sensitive C-reactive protein
HST	Human smoking topography

IB	Investigator's Brochure
ICF	Informed consent form
ICH	International Conference on Harmonization
INR	International normalized ratio
IOM	Institute of Medicine
IP	Investigational Product
IRB	Institutional Review Board
ISO	International Organization for Standardization
IU	International unit
IV	Intravenous
IWRS	Interactive Web Response System
LDH	Lactic dehydrogenase
LDL	Low density lipoprotein
LLN	Lower limit of the normal range
LLOQ	Lower Limit of Quantification
LOCF	Last observation carried forward
mCC	Menthol conventional cigarette
MCEQ	Modified Cigarette Evaluation Questionnaire
MCH	Mean corpuscular hemoglobin
MCHC	Mean corpuscular hemoglobin concentration
MCV	Mean corpuscular volume
MedDRA	Medical Dictionary for Regulatory Activities
MHBMA	Monohydroxybutenyl mercapturic acid
MNWS	Minnesota Nicotine Withdrawal Scale (revised version)
MR	Mean ratios
MRTP	Modified risk tobacco product
Neq	Nicotine equivalents
NNAL	4-(methylnitrosamino)-1-(3-pyridyl)-1-butanol
NNK	4-(methylnitrosamino)-1-(3-pyridyl)-1-butanone
NNN	N-nitrosonornicotine
NRT	Nicotine Replacement Therapy

Data and information contained in this document are considered to constitute trade secrets and confidential commercial information, and the legal protections provided to such trade secrets and confidential information are hereby claimed under the provisions of applicable law. No part of this document may be publicly disclosed without the written consent of Philip Morris Products S.A.

NSAID	Nonsteroidal Anti-inflammatory Drugs
o-tol	o-toluidine
PK	Pharmacokinetic(s)
PMI	Philip Morris International
PP	Per-protocol
PT	Prothrombin time
PX	Paraxanthine
QC	Quality control
QSU	Questionnaire of Smoking Urges (brief version)
RBC	Red blood cell (count)
RNA	Ribonucleic acid
SA	Smoking abstinence
SAE	Serious adverse event
SAP	Statistical analysis plan
S-BMA	S-benzylmercapturic acid
SDTM	Standards Consortium's Study Data Tabulation Model
SES	Socio-economic status
SHM	Sample handling manual
sICAM-1	Soluble inter-cellular adhesion molecule
SOC	System organ class
SOP	Standard Operating Procedure
S-PMA	S-phenylmercapturic acid
TC	Total cholesterol
TG	Triglycerides
THS	Tobacco Heating System
TPM	Total particulate matter
U	Urine sample required
UV	Ultra violet
████████	
ULN	Upper limit of the normal range

ULOQ	Upper limit of quantification
VAS	Visual analogue scale
WBC	White blood cell (count)
WHO	World Health Organization

Explanation of Terms

The following special terms are used in this protocol:

Baseline period	06:30 AM at Day -1 until 06:29 AM of Day 1.
Back up subject	Subjects who tested the product and were discontinued from enrollment.
Charger:	The function of the Charger (Model 4) is to recharge the Holder after use. It contains a battery with sufficient capacity to recharge the Holder approximately 20 times. It is a convenient size to carry around, and can itself be recharged from a mains power source.
Day 30 Visit, Day 60 Visit, and Day 90 Visit	Day 30 Visit, Day 60 Visit, and Day 90 Visit start on Day 30, Day 60, and Day 90 respectively at approximately 08:00 AM (check-in of the subject on site) until the check-out of the day after respectively on Day 31, Day 61, and the discharge on Day 91. This is to allow 24-hour urine collection.
End of study	End of Study is defined as the time of discharge on Day 91 (Day 90 Visit) of the subject plus 28 days of safety follow-up.
Enrolment	On Day -2 for eligible subjects after all applicable inclusion and exclusion criteria have been satisfactorily met and the subject is willing and ready to use the THS 2.2 Menthol (the trial of THS 2.2 Menthol is the last assessment prior to enrolment).
Exposure period in confinement	06:30 AM of Day 1 until time of Discharge on Day 6.
Exposure period in the ambulatory setting	From the time of discharge on Day 6 until the time of Discharge on Day 90 11:00 PM.

Investigator	Principal Investigator or sub-investigator
mCC	The term 'menthol conventional cigarette' refers to manufactured and commercially available menthol cigarettes and excludes hand-rolled cigarettes, cigars, pipes, bidis, and other nicotine-containing products.
mCC incompatible with HST SODIM® device	All mCCs that are incompatible with the HST SODIM® device (e.g., slim mCC).
Randomization	Assignment of the subject randomization number in the Interactive Web and Voice Response System. This can be done any time on Day 0, however, subjects are not to be informed of their randomization group and number prior Day 1.
Run-in period	Admission to site until 06:29 AM of Day -1.
Safety follow-up	After the time of Discharge on the Day 91, a 28-day safety follow-up will be done for the recording of spontaneously reported new AEs/SAEs and the active follow-up of ongoing AEs/SAEs by the site. In general, any AE will be followed-up until resolved, stabilized i.e. no worsening of the event, or a plausible explanation for the event has been found.
Screening failure	Subjects who do not meet the entry criteria from informed consent form (ICF) signature to the time of enrolment will be considered a screening failure and will be replaced by other subjects.
THS Menthol Tobacco Stick	The Menthol Tobacco Stick (product code C3 Menthol) contains tobacco which, when heated, generates an aerosol. It is custom-designed to be used with the Holder.
THS Tobacco Stick Holder (Holder)	The function of the Holder (Model 4.2) is to heat the Tobacco Stick, delivering an aerosol to the user. The electrical heating is powered from an internal battery which delivers power for about 6 minutes (allowing complete use of a single Menthol Tobacco Stick)

Time of Discharge	Time of Discharge on Day 6: time when the subject is released from the site (confinement period) after all the procedures of the day of discharge (Day 6) have been conducted prior to entering into the ambulatory period Time of Discharge on Day 91 (Day 90 Visit): time when the subject is released from the site on Day 91 and enters the 28-day safety follow-up period
Tobacco Heating Device	The Device comprises everything in THS 2.2 Menthol, except the Menthol Tobacco Stick
Tobacco Heating System 2.2 Menthol (THS 2.2 Menthol)	THS 2.2 Menthol comprises the following components: Menthol Tobacco Stick, Holder, Charger, a Cleaning Tool, a mains power supply, and a USB cable.

